2. SYNOPSIS

Name of Sponsor/Company:

Emalex Biosciences, Inc.

Name of Investigational Product:

Ecopipam Tablets

Protocol Number: EBS-101-CL-001

Title of Study:

A Multicenter, Placebo-Controlled, Double-Blind, Randomized, Parallel-Group, Phase 2b Study to Evaluate the Efficacy and Safety of Ecopipam Tablets in Children and Adolescent Subjects with Tourette's Syndrome

Study center(s): Approximately 60 sites in the United States, Canada, and the European Union

Principal Investigator: TBD

Investigators: TBD

Studied period (years):	Phase of development:
Estimated date first subject enrolled: Q2 2019	2b
Estimated date last subject completed: Q2 2022	

Objectives:

Primary:

The primary objective of this study is to evaluate the efficacy of ecopipam tablets in pediatric subjects (aged ≥ 6 to <18 years) with Tourette's Syndrome (TS).

Secondary:

The secondary objectives of this study are to evaluate the safety of ecopipam tablets in pediatric subjects (aged ≥ 6 to <18 years) with TS and characterize the pharmacokinetics (PK) of ecopipam.

Exploratory:

To evaluate the PK/pharmacodynamic relationship between plasma levels of ecopipam and treatment effect if possible.

Methodology:

This is a multicenter, placebo-controlled, double-blind, randomized, parallel-group, Phase 2b study in pediatric subjects (aged ≥ 6 to <18 years) with TS. Following a 28-day Screening period and Baseline visit, eligible subjects will be randomized 1:1 to receive either a target steady-state dose of 2 mg/kg/day ecopipam HCl or matching placebo for a 4-week Titration period followed by an 8-week Treatment period. Following titration, subjects who weigh 18 kg to ≤ 23 kg will receive a 37.5-mg active dose (or placebo), subjects who weigh >23 kg to ≤ 34 kg will receive a 50-mg active dose (or placebo), subjects who weigh >34 kg to ≤ 44 kg will receive a 75-mg active dose (or placebo), subjects who weigh >44 kg to ≤ 68 kg will receive a 100-mg active dose (or placebo), subjects who weigh >68 kg to ≤ 83 kg will receive a 150-mg active dose (or placebo), and subjects who weigh >83 kg will receive a 200-mg active dose (or placebo).

After the screening period, subjects will return to the clinic at Baseline and 4, 6, 8 and 12 weeks after Randomization. Study Visits at Weeks 4, 6, 8 and 12 after randomization may be completed in locations other than clinic and/or safety and efficacy assessments required at these visits will be made available for remote administration due to restrictions as a consequence of the COVID-19 pandemic or other qualifying event. Subjects will have telephone visits on Weeks 2 and 10 to assess adverse events and other safety parameters. Efficacy assessments will be conducted at Weeks 4, 6, 8 and 12. Safety assessments will be conducted at these visits as well. A Follow Up visit will be conducted in the clinic 7 and 14 days after the last dose of study medication. The follow up visits on Day 7 and 14 after the last dose of study medication may be completed in locations other than clinic and/or safety and efficacy assessments required at these visits will be made available for remote administration due to restrictions as a consequence of the COVID-19 pandemic or other qualifying event. Subjects will also be contacted 30 days after the last dose of study medication to determine any adverse events. At study completion or early termination, subjects will be tapered off study drug as outlined in the protocol.

An interim analysis will be conducted by an independent data safety monitoring board (DSMB) when 50% of the total subjects complete the study. The DSMB will determine the probability of a successful study (conditional power). If this probability is too small and does meet pre-specified criteria, the DSMB could recommend stopping the study for futility. If the probability of a successful study is reasonable, the DSMB can recommend continuing the study as planned. The DSMB can also recommend the continuation of the study with a sample size adjustment based on conditional power.

Sample Size Justification:

A sample size of 75 subjects per group will provide >80% power to detect difference between groups of 3 points on change from baseline the Yale Global Tic Severity Scale-Total Tic Score (YGTSS-TTS), with standard deviation = 6.1 and alpha = 0.05, assuming 10% drop out.

Number of subjects (planned):

75 per arm; 150 total

Diagnosis and main criteria for inclusion:

Inclusion Criteria:

- 1) Subject's parent or legal guardian must sign a written informed consent.
- 2) Subject must sign a written informed assent according to the requirements of the site's IRB/EC.
- 3) Subjects must be ≥ 6 to <18 years of age at time of screening.
- 4) Subjects must weigh ≥ 18 kg (39.6 lbs).
- 5) Subjects must have TS based on Diagnostic and Statistical Manual for Mental Disorders 5th Edition (DSM-5 diagnostic criteria) for TS.
- 6) Subjects must exhibit both motor and vocal tics that cause impairment with normal routines.
- 7) Subjects must have a minimum score of 20 on the YGTSS-TTS at Screening and at Baseline visits with tic symptoms in the investigator's judgment causing:
 - a. Subjective discomfort (e.g., pain or injury)
 - b. Sustained social problems (e.g., social isolation or bullying)
 - c. Social and emotional problems
 - d. Functional interference (e.g., impairment of academic achievements)
- 8) Subjects may not be taking any medications used to treat motor or vocal tics for at least 14 days prior to Baseline.

9) Adolescent females of childbearing potential who are sexually active must be using highly effective contraception (i.e., oral contraceptives, intrauterine device, intrauterine hormone-releasing system, bilateral tubal occlusion, vasectomized male partner) and agree to continue use of highly effective contraception for the duration

of their participation in the study. They must also agree to use highly effective contraception for 30 days after their last dose of study drug. 10) Sexually active male subjects must use a highly effective method of contraception during the study and agree to continue the use of highly effective contraception for at least 30 days after the last dose of study drug. 11) For subjects enrolled outside of the United States and Canada, the subject has received an adequate trial of non-pharmacological therapy without adequate response prior to study enrollment as documented by the Investigator. **Exclusion** Criteria: 1) Subjects with any unstable primary mood disorder (DSM-5 criteria) at Screening. 2) Subjects who have unstable medical illness or clinically significant abnormalities on laboratory tests, or ECG at Screening as determined by the Principal Investigator. 3) Subjects with a significant risk of committing suicide based on history, routine psychiatric status examination, investigator's judgment, or who had an answer of 'yes'' on any question other than 1–3 (currently or within the past 30 days) on the baseline/screening version of the Columbia Suicide Severity Rating Scale (C-SSRS). 4) Subjects with a clinical presentation at Screening and/or history consistent with another neurologic condition that may have had accompanying abnormal movements (e.g., Huntington's disease, Parkinson's disease, Wilson's disease, stroke, Restless Legs Syndrome). 5) Female subjects who are currently pregnant or lactating or planning to become pregnant during the course of the study. 6) Subjects who have moderate to severe renal insufficiency at Screening. 7) Subjects who have hepatic impairment at Screening 8) Subjects with current or recent (past 3 months) history of DSM-5 substance use disorder (with the exception of nicotine). 9) Subjects with positive urine drug screen for cocaine, amphetamine, methamphetamine, benzodiazepines, barbiturates, phencyclidine (PCP), or opiates at Screening, except those receiving stable, prescribed treatment for attention deficit/hyperactivity disorder (ADHD) 10) Subjects with a > 25% difference in the absolute change in YGTSS-TTS score between the Screening visit and the Baseline visit 11) Subjects with a lifetime history of bipolar disorder type I or II, dementia, schizophrenia, or any other psychotic disorder. 12) Subjects with a major depressive episode in the past 2 years. 13) Subjects with a history of attempted suicide. 14) Subjects with a history of seizures (excluding febrile seizures that occurred <2 years prior to Screening). 15) Subjects with a history of neuroleptic malignant syndrome. 16) Subjects with a myocardial infarction within 6 months. 17) Subjects who have had previous treatment with ecopipam. 18) Subjects who have had previous treatment with: • investigational medication within 1 month prior to Screening • depot neuroleptics within 3 months prior to Screening • oral neuroleptics within 4 weeks prior to Screening 19) Subjects receiving anti-depressant, anti-anxiety or anti-ADHD medications unless the dosage has been stable for a minimum of 4 weeks prior to Screening and not prescribed to relieve the neurological symptoms related to TS.

- 20) Subjects who have a need for medications which would have unfavorable interactions with ecopipam, e.g., dopamine antagonists or agonists [including bupropion], tetrabenazine, monoamine oxidase inhibitors, or St. John's Wort.
- 21) Initiation or changes in behavioral therapies for TS during the course of the study (i.e., Habit Reversal Training or Comprehensive Behavioral Intervention for Tics) as well as deep brain stimulation.
- 22) Subjects who have initiated new behavioral therapies fewer than 10 weeks prior to Baseline visit
- 23) Subjects unable to swallow tablets
- 24) Subjects with a known hypersensitivity to ecopipam or any of its excipients.
- 25) Any subject who in the opinion of the investigator is not a suitable candidate for the study.

Investigational product, dosage and mode of administration:

Ecopipam HCl 12.5-, 50-, 75- and 100-mg tablets; 2 mg/kg/day target dose; oral administration.

Dosing will be stratified by the following weight bands to better achieve the 2 mg/kg/day target dose: $\geq 18 - \leq 23 \text{ kg}$, $\geq 23 - \leq 34 \text{ kg}$, $\geq 34 - \leq 44 \text{ kg}$, $\geq 44 - \leq 68 \text{ kg}$, $\geq 68 - \leq 83 \text{ kg}$. Dosing will be based on the subject's weight at the Baseline and will not be adjusted if the subject's weight changes at subsequent Visits.

During the 4-week titration period, the following ecopipam HCl doses or matching placebo will be administered for each of the weight bands:

- Those who weigh ≥18-≤23 kg will titrate from 12.5 mg daily to 37.5 mg daily: 12.5 mg during Week 1, 25 mg during Week 2, and 37.5 mg during Weeks 3 and 4.
- Those who weigh >23-≤34 kg will titrate from 12.5 mg daily to 50 mg daily: 12.5 mg during Week 1, 25 mg during Week 2, 37.5 mg during Week 3 and 50 mg during Week 4.
- Those who weigh >34-≤44 kg will titrate from 12.5 mg daily to 75 mg daily: 12.5 mg during week 1, 25 mg during week 2, 50 mg during Week 3 and 75 mg during Week 4.
- Those who weigh >44-≤68 kg will titrate from 25 mg daily to 100 mg daily: 25 mg during Week 1, 50 mg during Week 2, 75 mg during Week 3 and 100 mg during Week 4.
- Those who weigh >68-≤83 kg will titrate from 25 mg daily to 150 mg daily: 25 mg during Week 1, 50 mg during Week 2, 100 mg during Week 3 and 150 mg during Week 4.
- Those who weigh >83 kg will titrate from 25 mg daily to 200 mg daily: 25 mg during Week 1, 50 mg during Week 2, 100 mg during Week 3, and 200 mg during Week 4.

During the 8-week treatment phase, the following ecopipam HCl doses or matching placebo will be administered for each of the weight bands:

- Those who weigh $\geq 18 \leq 23$ kg will receive 37.5 mg daily.
- Those who weigh $>23 \le 34$ will receive 50 mg daily.
- Those who weigh $>34 \le 44$ will receive 75 mg daily.
- Those who weigh $>44-\leq 68$ kg will receive 100 mg daily.
- Those who weigh $>68 \le 83$ kg will receive 150 mg daily.
- Those who weigh >83 kg will receive 200 mg daily.

All doses will be administered once daily in the evening.

At the end of the 8-week treatment phase, subjects will titrate off therapy and receive ecopipam HCl doses or matching placebo that will be reduced by 25 mg/day until off of drug; signs of symptoms of withdrawal will be monitored.

Duration of treatment:

Four weeks Screening Phase, Baseline Visit, 4-week Titration Period, 8-week Treatment Period and 2-week Follow-up Period. There will also be a phone call to subjects 30 days after study completion or early termination to assess any adverse events.

Reference therapy, dosage, and mode of administration:

Placebo-controlled, matching placebo tablets given by mouth (PO) in the evening.

Criteria for evaluation:

Efficacy:

Primary Efficacy Endpoint:

The primary efficacy endpoint is the change in the Yale Global Tic Severity Scale – Total Tic Score (YGTSS-TTS, i.e., sum of the motor and phonic tic scores) from baseline (YGTSS-TTS score from Baseline visit) to end of therapy (YGTSS-TTS score from Week 12).

Key Secondary Efficacy Endpoint:

• Change in Clinical Global Impression of Tourette Syndrome Severity (CGI-TS-S) from Baseline to Week 12

Other Secondary efficacy endpoints include:

- Change in Clinician Global Impression Tourette Syndrome of Improvement (CGI-TS-I) from Week 4 to Week 12
- Change in YGTSS-Global Score (GS) from Baseline to Week 12
- Change in Caregiver Global Impression of Change (CaGI-C) from Week 4 to Week 12
- Change in Gilles de la Tourette Syndrome–Quality of Life Scale for Children and Adolescents (C&A-GTS-QOL) from Baseline to Week12
- Percentage of subjects with a 25% improvement on the YGTSS-TTS
- Percentage of subjects with complete remission of tics on the YGTSS-TTS
- Change in YGTSS-TTS from Baseline to Weeks 4, 6, and 8
- Change in CGI-TS-S from Baseline to Weeks 4, 6, and 8
- Change in CGI-TS-I from Baseline to Weeks 4, 6, and 8
- Change in YGTSS-GS from Baseline to Weeks 4, 6, and 8
- Change in CaGI-C from Baseline to Weeks 4, 6, and 8
- Change in the C&A-GTS-QOL from Baseline to Weeks 4, 6, and 8

Rank order of hierarchy of the secondary endpoints will be outlined in the statistical analysis plan.

Safety:

Study Visits at Weeks 4, 6, 8 and 12 after randomization may be completed in locations other than clinic and/or safety assessments required at these visits will be made available for remote administration due to restrictions as a consequence of the COVID-19 pandemic or other qualifying event. Safety will be assessed by monitoring and recording all adverse events (AEs) and Serious Adverse Events (SAEs) (all Visits), regular monitoring of hematology, blood chemistry, and urine values (Screening, Baseline, Week 12 and 7 and 14 day Follow Up visits). HbA1c will be measured at the baseline and completion/early termination visits. Regular measurement of vital signs and the performance of a physical examination and an ECG will occur at Screening, Baseline and Weeks 4, 6, 8 and 12 and 7 and 14 day Follow Up visits. An additional assessment will include the Columbia-

Suicide Severity Rating Scale (C-SSRS) (all Visits except 30 day Follow up visit). Additional safety outcomes (Baseline and Weeks 4, 6, 8 and 12) will include the Abnormal Involuntary Movement Scale (AIMS), the Barnes Akathisia Rating Scale (BARS), the Swanson, Nolan and Pelham (SNAP-IV) questionnaire, the Children's Yale-Brown Obsessive Compulsive Scale (CY-BOCS), the Children's Depression Rating Scale-Revised (CDRS-R), the Giles de la Tourette Syndrome – Quality of Life Scale for Children and Adolescents (C&A-GTS-QOL) and the Pediatric Anxiety Rating Scale (PARS). Subjects will be monitored for signs of abuse, and withdrawal or dependence.

PK:

Blood samples will be collected to measure concentrations of ecopipam and/or its major (active) metabolites at Weeks 4 and 12. If visits at Weeks 4 and 12 are not conducted at a site due to restrictions as a consequence of the COVID-19 pandemic or other qualifying event, collection of PK samples is optional.

For the Week 4 visit, a morning appointment is suggested. Parents/caregivers will be instructed not to administer the study medication to the subject on the evening prior to the Week 4 visit and to record the time of administration of the last dose of study medication taken. The study drug administration will occur on the day of the Week 4 visit at the site under the supervision of the study investigator. An intravenous catheter will be placed, and the subject will have samples collected at the following time windows: one sample at pre-dose (34 to 44 hours since the last dose), one sample between 0.5 and 1.5 hour after administration of study medication, and one sample between 2 and 4 hours after study drug administration. Any samples should be collected at least 30 min apart.

For the Week 12 visit, parents/caregivers will be asked to record the time of study drug administration on the evening prior to the visit. An appointment is suggested to be made for the morning of the Week 12 visit. A blood sample will be collected at the end of the visit. The time of sample collection will be recorded. Blood samples will be processed as outlined in the protocol and serum/plasma will be frozen, shipped and analyzed for ecopipam and SCH40853.

Statistical methods:

Efficacy:

The Modified Intention-to-Treat (mITT) population will include all randomized subjects who received at least one dose of study drug. The mITT population will be used for the analysis of the efficacy endpoints.

The primary efficacy endpoint for this study will be the change from Baseline (YGTSS-TTS from Baseline) to end of therapy (YGTSS-TTS from Week 12).

The primary endpoint will be assessed with a Mixed Model for Repeated Measures (MMRM) model which will include fixed effects for treatment, visit (categorical week in study), interaction between treatment and visit, center and a covariate for baseline YGTSS-TTS. Taking consideration of missing data, multiple imputation or tipping point method may be used as a sensitivity analysis

Secondary endpoints will be evaluated in a similar manner with hierarchy to preserve alpha.

Additional analyses may need to be conducted for data not collected at sites and/or collected via remote administration due to restrictions as a consequence of the COVID-19 pandemic or other qualifying event, details of these additional analyses will be specified in the SAP.

The full details will be specified in the SAP.

Safety:

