13.2. Planned Analysis

13.2.1. Efficacy Analysis

The primary efficacy endpoint for this study will be the change from Baseline (score of YGTSS-TTS at Baseline) to end of therapy (score of YGTSS-TTS at Week 12). The analysis of primary efficacy endpoint will be performed in mITT and PP populations according to the randomized treatment.

The primary endpoint will be assessed with a Mixed Model for Repeated Measures (MMRM) model using (SAS MIXED procedure with REPEATED statement) with no imputation. The model will include fixed effects for treatment, visit interaction between treatment and visit, center, and covariate for baseline YGTSS-TTS score. If the sample size has been increased as a result of the interim analysis, the CHW (Cui-Hung-Wang) method will be used to control the type 1 error in the MMRM model. Taking consideration of missing data, multiple imputation or tipping point method may be used as a sensitivity analysis.

YGTSS-Global Score (YGTSS-GS), Clinical Global Impression of Tourette Syndrome Severity (CGI-TS-S), Clinical Global Impression of Tourette Syndrome Improvement (CGI-TS-I),

Caregiver Clinical Global Impression of Change (CaGI-C) and C&A-GTS-QOL will be analyzed using MMRM if appropriate. The treatment difference at Week 4, 8 and 12 can be estimated based on MMRM.

The percentage of subjects with a 25% improvement on the YGTSS-TS can be analyzed using Fisher Exact test.

All secondary endpoints will be analyzed in the mITT population according to randomized treatment.

All efficacy endpoints may also be summarized by treatment group. The fixed-sequence statistical strategy will be used to test all efficacy endpoints in a predefined rank order hierarchy which will be outlined in the SAP.

The full details and any sensitivity analyses will be specified in the SAP.

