8.1. Primary Efficacy Endpoint and Analysis

8.1.1. Primary Efficacy Analysis

The Yale Global Tic Severity Scale (YGTSS) is a clinician-completed rating scale used to quantify overall tic severity as well as specific subdomains of tic number, frequency, duration, intensity, and complexity. Each of these subdomains is scored, on a 5-point scale, separately for motor and vocal tics and then summed across both motor and vocal tics to yield a total tic score (TTS) ranging from 0 to 50. The YGTSS also provides for an overall impairment rating (0 = "none" to 50 = "severe"). The YGTSS has demonstrated acceptable internal consistency, good interrater reliability, and acceptable convergent and divergent validity.

YGTSS will be assessed at Screening, Baseline and at Weeks 4, 6, 8 and 12.

The primary efficacy endpoint for this trial will be the change from Baseline (score of YGTSS-TTS {i.e., sum of the motor and phonic tic scores} at Baseline) to end of therapy (score of YGTSS-TTS at Week 12). The analysis of primary efficacy endpoint will use the MITT set. Results for the PP set will also be provided.

Statistical analysis:

The primary endpoint will be analyzed with a Mixed Model for Repeated Measures (MMRM) model using the SAS MIXED procedure with REPEATED statement. The model will include fixed effects for treatment, visit, interaction between treatment and visit, region, age group (0 = children 6-11, 1 = adolescents 12-17) and covariate for baseline YGTSS-TTS.

If there is no sample size increase at the interim analysis, then a single MMRM based on all the data will be performed. However, if the sample size is increased from the planned (150) then two MMRM models will be performed and combined using the CHW (Cui-Hung-Wang) method, which controls the type 1 error, one MMRM model on the data from Stage 1 (the interim analysis data) and the second on data from Stage 2 (post-interim data). Information on treatment effect from the two stages will be combined in the weighted test-statistic:

$$T_{CHW} = \sqrt{\frac{n_1}{N}} T_1 + \sqrt{\frac{n_2}{N}} T_2$$

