8.1.2. Sensitivity Analysis

The primary efficacy analysis on change in the YGTSS-TTS at week 12 is to use MMRM model using all observed data. This model is appropriate when data is missing at random (MAR). To assess the robustness of the primary efficacy analysis, the following additional sensitivity analyses for missing data will be included for the mITT set:

- 1. Missing at Random (MAR) predictive mean matching multiple imputation method
- 2. Missing Not at Random (MNAR) jump to reference multiple imputation method
- 3. Tipping point under MNAR assumption

Details of sensitivity analysis for missing data and the statistical model are explained below.

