10.10. COVID-19 Analyses

Due to COVID-19 pandemic, additional analyses will be conducted:

- Listings of COVID-19 related study disruptions by subject and by site, including descriptions of the disruption.
- The amount of missing data by treatment group and overall by endpoint for data missing due to COVID-19 will be summarized in a table.
- Protocol deviations due to COVID-19 will be summarized by type and treatment in a table.

11. Interim Analyses

An unblinded interim analysis will be conducted when approximately 50% of the 150 planned subjects have been randomized (1:1 ratio between ecopipam and placebo) and completed treatment or are terminated early. The interim analysis will be performed by an independent statistician and governed by an external Data Safety Monitoring Board (DSMB). The conditional power will be calculated to help the DSMB assess the probability of a successful study based on observed data.

The primary efficacy endpoint of the study is the YGTSS-TTS. A smaller YGTSS-TTS score indicates a better condition in subjects with Tourette's syndrome, and we may expect that the ecopipam group has a larger reduction than the placebo group. Let μ_{σ} be the mean change YGTSS-TTS score from Baseline to Week 12 for the ecopipam group, and μ_p be the mean change YGTSS-TTS score from Baseline to Week 12 for the placebo group. Then, given $H_0: \mu_{\sigma} \ge \mu_p \equiv \Delta_{\sigma-p} \ge 0$ vs. $H_1: \mu_{\sigma} < \mu_p \equiv \Delta_{\sigma-p} < 0$. Since the original sample size calculation is based on two-sided test at a significance level of α =5%, we will use $\alpha/2$ =2.5% to match the one-sided test.

The primary endpoint will be analyzed with a Mixed Model for Repeated Measures (MMRM) model using the SAS MIXED procedure with REPEATED statement. The model will include fixed effects for treatment, visit, visit interaction between treatment and visit, region, age group (0 = children 6-11, 1 = adolescents 12-17) and covariate for baseline YGTSS-TTS.

To determine if the total sample size should be increased from N (to N^*), the conditional power based on the MMRM will be calculated at the interim analysis using the observed effects (where n=75) and the planned sample size (N=150).

If it is determined that the sample size should be increased, the CHW (Cui-Hung-Wang) statistic, which controls the type I error, will be used. The CHW statistic is a weighted statistic defined as:

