14.5. Tipping Point Analysis

Let delta1 and delta2 be the penalty to ecopipam group and reward for placebo group, respectively. Delta1 and delta2 = 1 to 10 (or estimated treatment effect from primary analysis if it is larger than 10) in step of 1. General steps for this analysis includes:

Step 1:

For each combination of (delta1, delta2), 100 imputations will be created.

In order to induce monotonicity, an imputation model will first be used to impute missing values for TTS of the YGTSS week 4 change values and will use age group at baseline, treatment arm, and baseline TTS score to determine the scores.

The SAS code for the imputation is as follows:

```
proc mi data=final out=mi seed=666 nimpute=100;
class agegrp region1 arm;
var agegrp region1 arm base _4;
monotone regpmm; run;
```

* Create delta1, delta2 in the dataset;

```
data mitv1;
set mi;
do i=1 to 10;
do j=1 to 10;
delta1=i; delta2=j; output;
end;
end;
run;
```

```
data mitv1;
set mitv1;
if firstdrp=4 and missdm in ("MNAR') and index(arm, 'ecopipam') then _&cv=_&cv+delta1;
else if firstdrp=4 and missdm in ("MNAR') and arm='Placebo' then _&cv=_&cv-delta2;
run;
```

For each visit after week 4: %macro tippimp (cv, pv, pvs, seed);

```
proc mi data=mitv&pv out=mitv¤tv seed=&seed nimpute=1;
class agegrp region1 arm;
var agegrp region1 arm base _&cv &pvs;
monotone regpmm;
by _Imputation_ &delta1 &delta2; run;
data mitv&cv;
```

```
if firstdrp=&cv and missdm in ("MNAR') and index(arm, 'ecopipam') then _&cv=_&cv+delta1;
else if firstdrp=&cv and missdm in ("MNAR') and arm='Placebo' then _&cv=_&cv-delta2;
run;
%mend;
```

```
% tippimp (6, 4, _4 , 2626);
% tippimp (8, 6, 4, %str(_4 _6), 2828);
% tippimp (12, 8, 6, 4 %str(_4 _6 _8), 2929);
```

Step 2

The resultant complete data sets will be analyzed using the same model as the primary analysis. The SAS code is as follows:

proc sort data=mitv12; by delta1 delta2 _imputation_ descending arm avisitn; run;

proc mixed data=all order=data; by delta1 delta2 _imputation_; class usubjid arm avisitn agegrp region1; model chg=arm avisitn arm*avisitn agegrp region1 base / ddfm=sat; repeated avisitn / type=un subject=usubjid; Ismeans arm*avisitn / diff cl; ods output diffs=diff(where=(avisitn=_avisitn) Ismeans=Ism; run;

```
Step 3
```

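### The primary MMRM imposes one baseline YGTSS-TTS slope on Weeks 4, 6, 8 and 12; adding baseline-by-visit is a cheap safeguard against a conditional, probably small, bias at Week 12

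*Protocol*

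**What the plan says.** The operative text is SAP 8.1.1, which lists "interaction between treatment and visit, region, age group (0 = children 6-11, 1 = adolescents 12-17) and covariate for baseline YGTSS-TTS" after the treatment and visit effects. The code in SAP 14.5, given there as the primary model, confirms the reading: "model chg=arm avisitn arm*avisitn agegrp region1 base / ddfm=sat", with "repeated avisitn / type=un subject=usubjid". SAP 11 repeats the model for the interim analysis, again with a single "covariate for baseline YGTSS-TTS".

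Protocol 13.2.1 has "visit interaction between treatment and visit, center, and covariate for baseline YGTSS-TTS score", and the synopsis agrees with it: "fixed effects for treatment, visit (categorical week in study), interaction between treatment and visit, center and a covariate for baseline YGTSS-TTS". Both use center where the SAP uses region and age group; that difference is a separate matter. No baseline-by-visit term appears in either document.

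SAP 8.1.2 says the primary analysis uses all observed data and adds: "This model is appropriate when data is missing at random (MAR".

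**The concern.** With a treatment-by-visit term and an unstructured covariance, the model is flexible in everything except baseline. It assumes that baseline severity predicts the change at Week 12 with the same slope as at Week 4. In a condition that the protocol describes as waxing and waning, a baseline score may well predict a near visit better than a distant one. The single fitted slope would then be a compromise across visits and would be wrong at Week 12, the primary time point.

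This matters because an observed-data MMRM infers the Week 12 outcome of children who leave from their baseline and earlier scores. If the slope is wrong and the leavers differ in baseline severity between arms, the errors do not cancel in the treatment difference. Dropout that depends only on baseline is a missing-at-random mechanism, so the assurance in SAP 8.1.2 would not be secured. Even without such dropout, a compromise slope removes less Week 12 variance than it could.

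**Working it through.** **1. The plan's own figure.** Inputs (Protocol 13.3, SAP 3.5): 75 per arm, difference 3, SD 6.1, alpha 0.05 (two-sided, SAP 11), 10% dropout. Evaluable: 75 × 0.9 = 67.5 per arm. Power = Φ(3 / (6.1√(2/n)) − 1.96), which is 81.2% for n = 67 and 81.8% for n = 68. For 80% power, n = 2(1.96 + 0.842)² × 6.1² / 3² = 64.9, so 65 per arm; 65 / 0.9 = 72.2, so 73. The stated power above 80% reproduces. It uses no covariate, so the slope question does not touch it.

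**2. What the documents say about the slope.** The earlier paediatric crossover study (Protocol 5.2.2.1) gives baseline and change SDs. If baseline and post-baseline variances are equal (an assumption), the correlation, which is also the slope of the post-baseline score on baseline, is ρ = 1 − SD_change² / (2 × SD_baseline²).

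- Placebo, Day 16: 1 − 4.7² / (2 × 6.7²) = 0.75; Day 30: 1 − 5.8² / (2 × 6.7²) = 0.63.
- Ecopipam, Day 16: 1 − 8.5² / (2 × 7.1²) = 0.28; Day 30: 1 − 8.7² / (2 × 7.1²) = 0.25.
- This trial's planned change SD of 6.1, with baseline SD 6.7 to 7.1: 0.59 to 0.63.

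The slope falls on placebo, is nearly flat on drug, and the planned SD is close to the Day 30 placebo value.

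**3. Bias at Week 12.** The documents give no formula, so this was simulated with 1,000,000 subjects per setting, fitting the MMRM by maximum likelihood with unstructured covariance. Assumptions: baseline SD 7.0; change SD 6.1; true Week 12 effect −3; dropout only after Week 4; log-odds of leaving changing by 1 per baseline SD where dropout depends on baseline; age and region omitted. Assumed slopes of change on baseline, Week 4 to Week 12: equal (−0.4 throughout), mild (−0.25 to −0.40), moderate (−0.1 to −0.4), extreme (0 to −0.6).

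Bias of the common-slope model, in points, at 10% dropout overall:

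| Baseline-related dropout | Equal | Mild | Moderate | Extreme |
|---|---|---|---|---|
| Same in both arms | none | none | none | none |
| Ecopipam only | none | 0.08 | 0.14 | 0.16 |
| Opposite directions by arm | none | 0.13 | 0.25 | 0.30 |
| Same dependence, 5% placebo vs 15% ecopipam | none | 0.08 | 0.10 | 0.15 |

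Entries marked none are within 0.03, which is simulation error. With baseline-by-visit added, bias is at most about 0.03 in every setting. At 20% dropout the opposite-directions row becomes 0.25, 0.49 and 0.66.

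The sign here was towards no effect, because severe children left ecopipam and milder children left placebo. Reversing who leaves reverses it.

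**4. The two ends of the range.** Taking slopes from step 2 that fit the planned SD (0.625 falling to 0.586) with opposite-direction dropout at 10%, the bias is about 0.05 points, under 2% of 3. A steeper assumption, 0.65 falling to 0.30 with SD 6.9, gave up to 0.47. That slope implies a Week 12 change SD of 6.9 × √(2 × (1 − 0.30)) = 8.2, well above 6.1.

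**5. Precision.** Simulated at 150 subjects, 1,500 trials per setting, with no dropout or 10% random dropout. Ratio of Week 12 standard errors, common slope over baseline-by-visit: equal 1.000; mild 1.003 to 1.004; moderate 1.011 to 1.015; extreme 1.010 to 1.023, with an empirical SD ratio up to 1.037. Example (moderate, 10% random dropout): SE 0.934 against 0.921, power 88.5% against 89.3%. With moderate slopes and opposite-direction dropout, the mean estimate is −2.76 against −2.99 and power 84.2% against 89.6%.

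**The case against.** The strongest case against acting is that the damage needs two conditions, and the documents establish neither.

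- **Slope.** The cited data stop at Day 30, which is about the first MMRM visit, so any drift over Weeks 4 to 12 is extrapolation. They also fit a constant slope: a change slope of −0.25 at both days with residual SDs of 4.4 and 5.5 gives change SDs of √(0.25² × 6.7² + 4.4²) = 4.7 and √(0.25² × 6.7² + 5.5²) = 5.7, close to the reported 4.7 and 5.8. This stands. The drift is plausible, not shown.
- **Dropout.** Protocol 7.4 and 10.5 withdraw children who cannot tolerate the dose, and Protocol 7.5 lists inadequate effect as a reason for leaving. These make arm differences in dropout likely, but nothing links dropout to baseline severity. This stands too.
- **Sensitivity analysis.** The MAR imputation in SAP 8.1.2.1 and 14.3 imputes each visit from arm, baseline and the other visits, so it allows visit-specific baseline relations. Analysing the completed data with a common slope is harmless, because randomisation balances baseline. This is real partial cover. But it is only a sensitivity analysis, and if it disagreed with the primary result, slope misspecification would be one unseparated explanation.
- **Estimand.** SAP 4.1.1 describes placebo-based imputation of Week 12 for some discontinuations, while SAP 8.1.2 uses observed data only. If the former governs, fewer leavers depend on the MMRM slope. The two sections need reconciling.

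A reader might infer that the Week 12 estimate is biased whenever dropout depends on baseline, that the bias favours ecopipam, or that precision is always lost. None of these follows. Identical baseline-related dropout in both arms cancels in the difference, the sign depends on who leaves, and with equal slopes the two models agree.

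**Conclusion.** The common-slope restriction is in every statement of the primary model and in the code. It is a cheap point to improve, not a demonstrated flaw in the primary result. Bias requires both a slope that changes across Weeks 4 to 12 and baseline-related dropout that differs by arm. At 10% dropout its size is about 0.05 to 0.3 points in either direction, against a planned 3; larger values at that rate need a Week 12 change SD well above 6.1. The standard-error cost under random dropout is roughly 0.3 to 4%, and only if slopes differ.

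These figures rest on assumed slopes and dropout patterns that the documents do not give. What can be said without those assumptions is that the missing-at-random assurance in SAP 8.1.2 also depends on a constant baseline slope, which the plan neither states nor supports. Nothing in the objections makes the common-slope model preferable.

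**What to change.** Add baseline YGTSS-TTS by visit to the primary model in SAP 8.1.1, the interim model in SAP 11 and the code in SAP 14.5: `model chg = arm avisitn arm*avisitn agegrp region1 base base*avisitn`. Do the same, with each scale's own baseline, for the continuous secondary MMRMs that have a baseline: CGI-TS-S, YGTSS-GS and C&A-GTS-QOL. Align the synopsis and Protocol 13.2.1, and make the change before unblinding.

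The cost is three degrees of freedom and some wording, with no new data and no change to the 75 per arm. If the slopes are in fact equal, essentially nothing is lost: the ratio of the estimate's SD, common slope over baseline-by-visit, was 0.998 to 1.000 in simulation.
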